### Revision Chronology

GlaxoSmithKline Document Number	Date	Version
2015N237824_00	2015-JUN-15	Original
2015N237824_01	2015-JUL-03	Amendment No. 1
To amend the eligibility criteria		
2015N237824_02	2015-NOV-24	Amendment No. 2
To clarify some ambiguous text in the protocol		
2015N237824_03	2016-APR-22	Amendment No. 3
To include iPAH patients with QTcF interval up to and including 500 msec.		

Copyright 2016 the GlaxoSmithKline group of companies. All rights reserved.  
 Unauthorised copying or use of this information is prohibited.

## 1. PROTOCOL SYNOPSIS FOR STUDY 204746

### Rationale

Pulmonary Arterial Hypertension (PAH) used to be considered primarily a consequence of abnormal pulmonary vasoconstriction, but is now regarded as a disease caused mainly by pulmonary vascular remodelling with features analogous to carcinogenesis [Guignabert, 2013].

The currently available PAH therapies are vasodilators and provide symptomatic support but do not fully address the underlying remodelling aspects of the disease where there is a significant unmet need for a specific disease modifying PAH therapy.

In 2011, Novartis submitted an application for use of imatinib (Ruvise), a tyrosine kinase inhibitor, as an add-on therapy for the treatment of pulmonary arterial hypertension (PAH) to improve exercise capacity in patients with pulmonary vascular resistance who remain symptomatic on dual vasodilator therapy. This was based on early clinical data indicating improvements in PVR/PAP. This medicine would have been the first disease-modifying treatment for PAH, but failed to receive a positive opinion (lack of sufficient positive risk/benefit evidence) and Novartis withdrew their application in January 2013.

GSK has identified the FAK inhibitor, GSK2256098, currently in development for glioblastoma as a candidate for repurposing for PAH.

Focal adhesion kinase (FAK) is a non-receptor kinase intracellular signalling node which is important for the initiation and maintenance of vascular smooth muscle cell (SMC) switching to the synthetic phenotype. GSK also has *in vitro* tissue cell data showing pulmonary artery smooth muscle cell migration effects, further demonstration of the target in disease relevant tissues is important before proceeding to a clinical Ph II study in PAH patients.

Therefore, a PET imaging study using a microdose of a C-radiolabelled FAK tyrosine kinase inhibitor (TKI) GSK2256098 will enable identification of the cardiopulmonary sites where there is both expression of autoactivated, signalling-ready, FAK and drug exposure. The uptake of C –GSK2256098 within the lung and / or heart will inform the decision as to whether a follow-on phase 2 trial should be initiated to investigate the therapeutic utility of GSK2256098 in iPAH.

## Objective(s)/Endpoint(s)

Objectives	Endpoints
Primary	

 
To compare the uptake of [C]-GSK2256098 in the heart and lungs of PAH patients versus the heart and lungs of healthy control subjects
 
	
 
Uptake of [C]-GSK2256098 in the heart and lung (assessed as the volume of distribution(<math>V_T</math>) and/or standardised uptake values (SUV) as measured by PET
 

Exploratory	

 
To explore the spatial distribution of [C]-GSK2256098 uptake in the heart and lungs of PAH patients versus the heart and lungs of healthy control subjects.
 
	
 
Qualitative assessment of the spatial distribution of [C]-GSK2256098 uptake in the heart and lungs
 

## Overall Design

- This will be a cross-sectional study exploring the uptake of [C]-GSK2256098 in PAH patients and in healthy (age and gender-matched) volunteers.
- This is a non-randomised, open label study where all volunteers will receive one microdose of the radiolabelled compound.

## Treatment Arms and Duration

- The total duration of the study for each subject will be approximately 2 months from screening to follow-up. The screening period will be followed by 1 scanning day and the follow-up visit.
- All subjects will receive one microdose of [C]-GSK2256098. The maximum amount of radioactivity injected during the -PET scan will be 500 MBq and maximum mass of [C]-GSK2256098 administered will be  $\leq 10\mu\text{g}$ .
- Subject completion for the primary endpoint is defined as a subject who completes the PET-CT scan visit.

## Type and Number of Subjects

- Up to 12 healthy subjects and 12 PAH patients will be enrolled to provide sufficient PET data to quantify the uptake of [C]-GSK2256098 in the heart and lungs.
- If subjects prematurely discontinue the study, additional subjects may be enrolled as replacement subjects at the discretion of the Investigator/GSK Medical Monitor

## Analysis

### Hypotheses

Although a valid scientific hypothesis underpins this study, as expressed in the study objectives (viz: “FAK inhibitor uptake is substantially higher in patients than in (relatively) well-matched healthy control subjects”), no statistical hypothesis testing will be conducted, nor will any p-values be generated. (It would make no sense to “reject” a null hypothesis of “no difference in FAK expression between patients and healthy volunteers (HVs)” in the absence of a pre-specified threshold of clinical relevance.)

Instead, we will adopt an estimation approach, and use simple Bayesian methods to quantify the evidence which the study generates about the endpoints themselves, and about contrasts (probably ratios) of those endpoints. We will evaluate the evidence in as close to real-time as is feasible.

### Sample Size Considerations

There is little known about the likely mean values of the PET-derived functional primary endpoints (Volume of distribution, and/or some form of integrated SUV) in this population. Therefore our sample size is driven by a mixture of (i) what is known about between-subject variability from relevant, recent PET studies, (ii) feasibility, and (iii) flexibility.

An ongoing study investigating the validation and dosimetry of a PET ligand in healthy subjects and patients with IPF (study RES116235) has been able to draw firm conclusions about similar endpoints (in terms of the estimation methods we describe below) using around 5 subjects. Therefore we will set five patients and five age- and gender-matched HVs as our initial target sample size.

From that point onwards, the data will be monitored continuously (or as near as possible given practicalities of study operationalisation), and at each step the following decisions will be made:

- Stop, and conclude that there is strong evidence of differential FAK uptake (as measured by the study endpoints) between patients and HVs.
- Stop, and conclude that there is insufficient evidence of any great difference, and furthermore (conditional on observed data i.e. in a formal Bayesian sense) there is low probability that an increase in sample size will reverse such a conclusion
- Continue to enrol patient-HV pairs, and re-evaluate the decision.

This iterative cycle will be followed up until a maximum of twelve patients and twelve HVs have been recruited into the study.

## 2. INTRODUCTION

GSK2256098 is a FAK inhibitor being considered for the treatment PAH.

### 2.1. Study Rationale

Focal adhesion kinase (FAK) is a non-receptor kinase intracellular signalling node which is important for the initiation and maintenance of vascular SMC switching to the synthetic phenotype. GSK also has *in vitro* tissue cell data showing pulmonary artery smooth muscle cell migration effects, further demonstration of the target in disease relevant tissues is important before proceeding to a clinical Ph II study in PAH patients.

Therefore, a PET imaging study using a microdose of a C-radiolabelled FAK tyrosine kinase inhibitor (TKI) GSK2256098 will enable identification of the cardiopulmonary sites where there is both expression of autoactivated, signalling-ready, FAK and drug exposure. The uptake of C –GSK2256098 within the lung and / or heart will inform the decision as to whether a follow-on phase 2 trial should be initiated to investigate the therapeutic utility of GSK2256098 in iPAH.

### 2.2. Brief Background

Pulmonary Arterial Hypertension (PAH) used to be considered primarily a consequence of abnormal pulmonary vasoconstriction, but is now regarded as a disease caused mainly by pulmonary vascular remodelling with features analogous to carcinogenesis [Guignabert, 2013].

The currently available PAH therapies are vasodilators and provide symptomatic support but do not fully address the underlying remodelling aspects of the disease where there is a significant unmet need for a specific disease modifying PAH therapy. This is particularly important since increasing pulmonary artery pressures leads to progressive, and sometimes maladaptive, right ventricle remodelling which increases the risk of QTcF interval prolongation (Rich, 2013), and is probably one of the factors which contributes to the increased risk of sudden death in this population.

In 2011, Novartis submitted an application for use of imatinib (Ruvise), a tyrosine kinase inhibitor, as an add-on therapy for the treatment of pulmonary arterial hypertension (PAH) to improve exercise capacity in patients with pulmonary vascular resistance who remain symptomatic on dual vasodilator therapy. This was based on early clinical data indicating improvements in PVR/PAP. This medicine would have been the first disease-modifying treatment for PAH, but failed to receive a positive opinion, due to lack of positive risk/benefit and Novartis withdrew their application in January 2013.

GSK has identified the FAK inhibitor, GSK2256098, currently in development for glioblastoma as a candidate for repurposing for PAH.

### 3. OBJECTIVE(S) AND ENDPOINT(S)

Objectives	Endpoints
Primary	

 
To compare the uptake of [C]-GSK2256098 in the heart and lungs of PAH patients versus the heart and lungs of healthy control subjects
 
	
 
Uptake of [C]-GSK2256098 in the heart and lung (assessed as the volume of distribution(<math>V_T</math>) and/or standardised uptake values (SUV)) as measured by PET
 

Exploratory	

 
To explore the spatial distribution of [C]-GSK2256098 uptake in the heart and lungs of PAH patients versus the heart and lungs of healthy control subjects.
 
	
 
Qualitative assessment of the spatial distribution of [C]-GSK2256098 uptake in the heart and lungs
 

### 4. STUDY DESIGN

#### 4.1. Overall Design

- This will be a cross-sectional study exploring the uptake of [C]-GSK2256098 in PAH patients and in healthy (age and gender-matched) volunteers.
- This is a non-randomised, open label study where all volunteers will receive one microdose of the radiolabelled compound.

#### 4.2. Treatment Arms and Duration

- The total duration of the study for each subject will be approximately 2 months from screening to follow-up. The screening period will be followed by 1 scanning day and the follow-up visit.
- All subjects will receive one microdose of [C]-GSK2256098. The maximum amount of radioactivity injected during the -PET scan will be 500 MBq and maximum mass of [C]-GSK2256098 administered will be  $\leq 10\mu\text{g}$ .

#### 4.3. Type and Number of Subjects

- Up to 12 healthy subjects and 12 PAH patients (including those with a prolonged QTcF interval  $\leq 500\text{ms}$ ) will be enrolled to provide sufficient PET data to quantify the uptake of [C]-GSK2256098 in the heart and lungs.
- If subjects prematurely discontinue the study, additional subjects may be enrolled as replacement subjects at the discretion of the Investigator/GSK Medical Monitor.

#### **4.4. Design Justification**

The study will be open-label and non-randomised as there is no intention of performing inference about the safety or efficacy profile of an NCE or other test therapeutic vs any form of control. A sufficient number of subjects will be recruited, based on feasibility, to permit adequate quantification of the uptake of [C]-GSK2256098 in target organs within the patient population, and those levels of expression will be compared with those measured in a set of age and gender-matched healthy controls. This form of case matching is intended to reduce the variance in the estimate of uptake by imposing a form of biological control on the signal derived from the subjects.

#### **4.5. Benefit:Risk Assessment**

Summaries of findings from both clinical and non-clinical studies conducted with GSK2256098 can be found in the Investigator's Brochure. Of note the amount of GSK2256098 administered is a tracer dose and is not expected to result in any clinically significant pharmacology. The following section outlines the risk assessment and mitigation strategy for this protocol:

#### 4.5.1. Risk Assessment

Potential Risk of Clinical Significance	Summary of Data/Rationale for Risk	Mitigation Strategy
Study Procedures		
Subjects will be exposed to an additional dose of ionising radiation as a consequence of their participation in this study	The majority of the radiation dose comes from the administered radioligand, while a smaller portion comes from a low dose CT scan performed to estimate tissue attenuation.	
Subjects < 40 years will not be eligible for the study.
 
In addition, the study will exclude subjects who have previously participated in a research protocol involving nuclear medicine, PET and/or HRCT or radiological investigations or occupational exposure resulting in radiation exposure greater than 10 mSv over the past 3 years or greater than 10 mSv in a single year including the proposed study (clinical exposure from which the subject receives potential direct benefit is not included in these calculations).
 
The study will exclude women of childbearing potential.
 
The maximal dose of ionising radiation that subjects in this study may be exposed to is outlined in Appendix 5.

Arterial cannulation	Arterial blood for quantitative analysis will be sampled from a cannula in the radial artery.	Subject suitability to undergo radial artery cannulation will be assessed by means of an Allen's test assessment and testing the

Potential Risk of Clinical Significance	Summary of Data/Rationale for Risk	Mitigation Strategy
		
subjects blood coagulation profile. Arterial cannulation will be performed by suitably trained staff under local anaesthetic, using best practice. On completion of the PET scan, the radial artery cannula will be removed and subjects observed until haemostasis obtained. The PAH patients will be at an increased risk of bruising and will not be discharged until the Investigator is happy with the cannulation site. The total amount of blood collected for all of the study procedures will not exceed 500 mL.
 
Warfarin will be discontinued in subjects on prophylactic doses about 5 days before the arterial cannulation. Arterial cannulation will be performed with an INR ideally <math>\leq 2</math>. In situations where, anticoagulation is administered with a therapeutic intent (rather than simply prophylaxis), warfarin will be substituted by Low Molecular weight heparin starting up to 5 days prior to until a time after completion of the PET scan when therapeutic anti-coagulation is considered to have been achieved in the views of the clinician.

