
8. Male or Female
 
Males:
 
Male subjects with female partners of child bearing potential must comply with the following contraception requirements from the time of first dose of study medication until 3 months after the scan. In addition, they must not plan to father a child, or donate sperm, for 3 months after the scan.
 
a. Vasectomy with documentation of azoospermia.
 
b. Male condom plus partner use of one of the contraceptive options below:
 
 
• Contraceptive subdermal implant
 
• Intrauterine device or intrauterine system
 
• Oral Contraceptive, either combined or progestogen alone [Hatcher, 2007a] Injectable progestogen [Hatcher, 2007a]
 
• Contraceptive vaginal ring [Hatcher, 2007a]
 
• Percutaneous contraceptive patches [Hatcher, 2007a]
 
 
This is an all-inclusive list of those methods that meet the following GSK definition of highly effective: having a failure rate of less than 1% per year when used consistently and correctly and, when applicable, in accordance with the product label. For non-product methods (e.g., male sterility), the investigator determines what is consistent and correct use. The GSK definition is based on the definition provided by the ICH [ICH, M3 (R2) 2009].”
 
The investigator is responsible for ensuring that subjects understand how to properly use these methods of contraception.
 
Females:
 
a. Non-reproductive potential defined as:
 
 
• Pre-menopausal females with one of the following: 
 
• Documented tubal ligation
 
• Documented hysteroscopic tubal occlusion procedure with follow-up confirmation of bilateral tubal occlusion
 
• Hysterectomy
 
• Documented Bilateral Oophorectomy
 
 
 

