- Postmenopausal defined as 12 months of spontaneous amenorrhea in questionable cases a blood sample with simultaneous follicle stimulating hormone (FSH) and estradiol levels consistent with menopause (refer to laboratory reference ranges for confirmatory levels). Females on hormone replacement therapy (HRT) and whose menopausal status is in doubt will be required to use one of the highly effective contraception methods if they wish to continue their HRT during the study. Otherwise, they must discontinue HRT to allow confirmation of post-menopausal status prior to study enrolment.

The investigator is responsible for ensuring that subjects understand how to properly use these methods of contraception.

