
Females:
 
A female subject of non-child bearing potential is eligible to participate if she is not pregnant (as confirmed by a negative urine human chorionic gonadotrophin (hCG) test), not lactating, and at least one of the following conditions applies:
 

a. Non-reproductive potential defined as:

• Pre-menopausal females with one of the following:

• Documented tubal ligation

• Documented hysteroscopic tubal occlusion procedure with follow-up confirmation of bilateral tubal occlusion

• Hysterectomy

• Documented Bilateral Oophorectomy

• Postmenopausal defined as 12 months of spontaneous amenorrhea in questionable cases a blood sample with simultaneous follicle stimulating

hormone (FSH) and estradiol levels consistent with menopause (refer to laboratory reference ranges for confirmatory levels). Females on hormone replacement therapy (HRT) and whose menopausal status is in doubt will be required to use one of the highly effective contraception methods if they wish to continue their HRT during the study. Otherwise, they must discontinue HRT to allow confirmation of post-menopausal status prior to study enrolment.

The investigator is responsible for ensuring that subjects understand how to properly use these methods of contraception.

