#### **7.3.6. Clinical Safety Laboratory Assessments**

All protocol required laboratory assessments, as defined in [Table 1](#), must be conducted in accordance with the Laboratory Manual, and Protocol Time and Events Schedule.

Laboratory requisition forms must be completed and samples must be clearly labelled with the subject number, protocol number, site/centre number, and visit date. Details for the preparation and shipment of samples will be provided by the laboratory and are detailed in the site SOPs. Reference ranges for all safety parameters will be provided to the site by the laboratory responsible for the assessments.

If additional non-protocol specified laboratory assessments are performed at the institution's local laboratory and result in a change in subject management or are considered clinically significant by the investigator (e.g., SAE or AE or dose modification) the results must be recorded in the CRF.

Refer to the site SOPs for appropriate processing and handling of samples to avoid duplicate and/or additional blood draws.

Haematology, clinical chemistry, urinalysis and additional parameters to be tested are listed in [Table 1](#).

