**Table 1 Protocol Required Safety Laboratory Assessments**

Laboratory Assessments	Parameters			
Haematology	Platelet Count	RBC Indices:	WBC count with Differential:	
	RBC Count	MCV	Neutrophils	
	Hemoglobin	MCH	Lymphocytes	
	Hematocrit	MCHC	Monocytes	
			Eosinophils	
			Basophils	
Clinical Chemistry	BUN	Potassium	AST (SGOT)	Total and direct bilirubin
	Creatinine	Sodium	ALT (SGPT)	Total Protein
	Glucose	Calcium		Albumin
Routine Urinalysis	
 
Specific gravity
 
pH, glucose, protein, blood and ketones by dipstick
 
Microscopic examination (if blood or protein is abnormal)
 
			
Other Screening Tests	
 
HIV
 
Hepatitis B (HBsAg)
 
Hepatitis C (Hep C antibody)
 
FSH and estradiol (as needed in women of non-child bearing potential only)
 
Pregnancy test
 
Alcohol and drug screen (to include at minimum: amphetamines, barbiturates, cocaine, opiates, benzodiazepines and cannabinoids)
 
			

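### HRT users of unconfirmed menopausal status may be dosed with no pregnancy test required between screening and injection, and section 4.5.1 does not mention this exception

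*Protocol*

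**What the plan says.** Protocol section 4.5.1 (Risk Assessment) lists the safeguards against ionising radiation. One of them reads "The study will exclude women of childbearing potential". No exception is given.

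The eligibility sections restrict women to those of non-reproductive potential, then define that term. Within the postmenopausal part of the definition, 5.1.1 says that a woman on HRT "whose menopausal status is in doubt will be required to use one of the highly effective contraception methods if they wish to continue their HRT". Section 5.1.2 has the same provision for PAH patients: "whose menopausal status is in doubt will be required to use one of the highly effective contraception methods". In both sections, only women who do not take this route must stop HRT so that their status can be confirmed before enrolment.

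Pregnancy testing appears in two places:

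- In 5.1.2, a female PAH patient "is eligible to participate if she is not pregnant (as confirmed by a negative urine human chorionic gonadotrophin (hCG) test), not lactating". Section 5.1.1 has no matching sentence for healthy volunteers.
- Table 1 in section 7.3.6 lists "Pregnancy test" among the other screening tests, without limiting it to one group.

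Section 7.3.6 says that the Table 1 tests "must be conducted in accordance with the Laboratory Manual, and Protocol Time and Events Schedule", and section 7 makes the Time and Events Table the source of exact timing. That table (Protocol 7.1, repeated in SAP section 6) has no pregnancy-test row at any visit. Screening may take place up to 30 days before the scan.

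**The concern.** The risk assessment tells its reader that no woman who could be pregnant will receive the tracer and CT. The eligibility text delivers this for women with surgical sterility or confirmed menopause. For HRT users in doubt it replaces confirmation with contraception, which lowers the chance of pregnancy but does not detect one.

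A screening test finds a pregnancy that is present and detectable at screening. A pregnancy that begins later, or was too early to detect then, would not be looked for before exposure. Followed exactly, the plan allows a woman of unconfirmed status to be scanned up to 30 days after her last pregnancy check. What is at stake is an avoidable research exposure in pregnancy, in a study with no personal benefit to the participant.

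**Working it through.** The plan gives no figure on this point to reproduce. The check is a side-by-side reading, followed by a rough bound.

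**Step 1: what each section requires of an HRT user in doubt**

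| Place | Requirement |
|---|---|
| Protocol 4.5.1 | Women of childbearing potential excluded; no exception |
| Protocol 5.1.1 (healthy volunteers) | May stay on HRT with contraception; status not confirmed; no hCG or lactation criterion |
| Protocol 5.1.2 (PAH patients) | Same HRT provision; negative urine hCG and not lactating; no time point |
| Table 1 | Pregnancy test listed as a screening test |
| Time and Events Table (Protocol 7.1, SAP 6) | Pregnancy-test rows: 0 at screening, 0 at the scan, 0 at follow-up |
| Protocol 7.3.2 and Appendix 4 | Pregnancy collection covers female partners of male subjects only |

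**Step 2: what the missing row shows.** Taken alone, the absence of a screening row shows little. Table 1 also lists "FSH and estradiol (as needed in women of non-child bearing potential only"), and those tests have no row either, so the schedule does not itemise every screening test. The reasonable reading is that a pregnancy test is done at screening in both groups. The gap is the interval from screening to injection, for which no section requires a test. By contrast, the schedule does repeat the alcohol breath test and Allen's test on the scan day, and asks for an INR in patients who have been on warfarin.

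**Step 3: bound on conception in the interval.** Inputs:

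- Contraceptive failure rate. The protocol defines highly effective as "having a failure rate of less than 1% per year when used consistently and correctly". This definition and the list of methods stand under Males; I assume that they also apply to these women.
- Longest screening-to-scan interval: 30 days.
- Risk assumed even over the year.

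Per affected woman: 1% × 30/365 = 0.082%, as an upper bound.

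| Affected women (number assumed) | Upper bound |
|---|---|
| 0 | 0 |
| 1 | 0.082% |
| 2 | 0.16% |
| 3 | 0.25% |

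The documents do not give the size of the subgroup; the whole study has at most 12 + 12 = 24 subjects. A shorter interval lowers the bound proportionally. Imperfect use, or contraception started only at or after screening, raises it. A pregnancy already present but undetectable at screening lies outside the calculation.

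**Step 4: exposure.** Protocol Appendix 5 gives 6 µSv/MBq, a 500 MBq maximum and 1.2 mSv per CT:

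- Tracer: 500 × 6 = 3,000 µSv = 3.0 mSv
- With one CT: 3.0 + 1.2 = 4.2 mSv
- With a repeat CT: 3.0 + 2 × 1.2 = 5.4 mSv, which agrees with the protocol's total

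These are effective doses to the woman. No fetal dose is stated.

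**The case against.** The strongest reply is that there is no real contradiction. The HRT clause sits inside the definition of non-reproductive potential, 4.5.1 is a one-line summary in a risk table, and section 5 holds the working rule. Doubt about menopausal status in a woman aged 40 to 70 on HRT is not the same as childbearing potential, and the protocol meets that doubt with mandatory contraception. This largely stands. A reader might infer that the protocol openly admits women of childbearing potential against its own exclusion; the text does not go that far. What remains is that status may stay unconfirmed and that 4.5.1 is stated too absolutely.

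A second reply is that testing already exists. This also stands for screening. It would be wrong to infer that the protocol has no pregnancy testing, or that healthy volunteers go untested: Table 1 covers both groups, and a volunteer with a positive test would in practice fail other criteria. It does not answer the interval to the scan.

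A third reply is that a scan-day test could be added under sections 7 and 7.3, or may already be in the Laboratory Manual or site procedures. Sections 7 and 7.3 allow extra safety time points in response to newly available data; they do not require this one. The manual and site procedures are not available to check.

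Finally, the risk is close to nil. That is accepted, and it sets the weight of the point.

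**Conclusion.** The point holds as a minor subject-safety gap. Section 4.5.1 should carry a qualification, and an HRT user of unconfirmed status can be dosed with no pregnancy test required since screening.

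The subgroup is narrow and possibly empty. The bound of about 0.08% per affected woman rests on three assumptions: the failure-rate definition extends to women, contraception is used perfectly throughout, and risk is even over a full 30 days. A scan-day test would not find every very recent conception either, so it would narrow the gap without closing it.

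Two stronger inferences are not supported. The 4.2 to 5.4 mSv range should not be read as a measure of fetal harm: it is the woman's effective dose, part of it from a CT of the lung. Nor does anything here affect the comparison of uptake between patients and volunteers; the endpoint and the Bayesian analysis are untouched.

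The case for acting is that a safeguard stated in the risk assessment can be made good at very little cost. It does not rest on the frequency of the event.

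**What to change.** 1. Add a scan-day urine hCG to the Protocol Time and Events Table, before dosing, with a negative result required before CT and injection. Apply it only to HRT users whose post-menopausal status is unconfirmed. Women with documented surgical sterility or confirmed menopause need no scan-day test.
2. Add to 5.1.1 the 5.1.2 condition that a woman is not pregnant, shown by a negative urine hCG, and not lactating.
3. Qualify the 4.5.1 sentence so that it names the HRT exception and the pre-dose test that covers it.

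Adding a screening-visit row and updating the schedule copy in SAP section 6 would be tidy-up only.

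The cost is a protocol amendment and one extra urine test for few or no women. The option to continue HRT with contraception stays, so nobody has to stop HRT.
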